- (2) **Control Conditions Hypothesis:** We hypothesize significant differences in signal intensity across the three different epoch conditions—TM, passive-attending and mental-counting. Specifically, de-excitation will be maximum for TM, then passive-attending, and lastly, mental-counting.

Aim 2: Maximum De-excitation Meditation Substate. We predict that event-related (er-fMRI) and state-related (sr-fMRI) analytic procedures will yield distinct spatial and temporal patterns of BOLD intensity that characterize the maximum de-excitation substate associated with spontaneous breath-quiescent periods (SBQ, breath period > 10 sec). We will test five hypotheses in this experiment.

- (3) **IBH-Blood Gas Hypothesis:** Using event-related-fMRI, we hypothesize moderate changes in blood gas changes will be detected during Intentional Breath-Holding (IBH), and blood gas levels will be significantly correlated with changes in BOLD signal intensity, consistent with published findings.
- (4) **SBQ-Blood Gas Hypothesis:** Using event-related-fMRI, we hypothesize small changes in blood gas changes will be detected during Spontaneous Breath Quiescence (SBQ), and blood gas levels will not be significantly correlated with changes in BOLD signal intensity.
- (5) **SBQ-IBH Hypothesis:** Using event-related-fMRI, we hypothesize that specific spatiotemporal patterns of BOLD signal will be associated with onset of SBQ, and will differ from IBH control periods in terms of reduced BOLD signal of the anterior cingulate cortex and brainstem during SBQ.
- (6) **SBQ-Controls Hypothesis:** Using state-related-fMRI, we hypothesize that BOLD signal intensity patterns during SBQ periods will differ from two control conditions—IBH periods, and eyes-closed periods (as defined in Aim 1, either passive-attending or mental-counting).
- (7) **SBQ-Non-SBQ Hypothesis:** Using state-related-fMRI, we hypothesize that BOLD signal intensity patterns during SBQ periods will differ from the scans during non-SBQ periods during meditation.

B. BACKGROUND AND SIGNIFICANCE

B.1. Need for Basic Neuroscience Research on Mechanisms of CAM Modalities.

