D.6.1.1 IBH-Blood Gas Hypothesis. Using event-related-fMRI, we hypothesize moderate changes in blood gas changes will be detected during Intentional Breath-Holding (IBH), and blood gas levels will be significantly correlated with changes in BOLD signal intensity, consistent with published findings.

D.6.1.2 SBQ-Blood Gas Hypothesis. Using event-related-fMRI, we hypothesize small changes in blood gas changes will be detected during Spontaneous Breath Quiescence (SBQ), and blood gas levels will not be significantly correlated with changes in BOLD signal intensity.

D.6.1.3. SBQ-IBH Hypothesis. Using event-related-fMRI, we hypothesize that specific spatiotemporal patterns of BOLD signal will be associated with onset of Spontaneous Breath Quiescence (SBQ), and will

differ from IBH control periods as marked, in particular, by reduced BOLD signal of the anterior cingulate cortex and brainstem during SBQ.

D.6.1.4. SBQ-Controls Hypothesis. Using state-related-fMRI, we hypothesize that BOLD signal intensity patterns during SBQ periods will differ from two control conditions—IBH periods, and eyes-closed periods (as defined in Aim 1, either passive-attending or mental-counting).

D.6.1.5. SBQ-Non-SBQ Hypothesis: Using state-related-fMRI, we hypothesize that BOLD signal intensity patterns during SBQ periods will differ from the scans during non-SBQ periods during meditation.

D.6.2. Issues.

The second phase of the grant will systematically explore neural patterns underlying the second principal substate during TM practice—periods of SBQ with durations of 10 to 40 sec—signifying the maximum de-excited state of TM practice. A study of breath-quietness raises a number of possible confounds.

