- We expect minor blood gas changes and hence, few significant correlations between CO₂, with BOLD signal during spontaneous breath-quietness.

D.6.4.3. Neuroimages during SBQ and IBH. Er-fMRI will be compared between IBH and SBQ periods, using a repeated measures MANOVA.

- We expect main effects for brain areas. Animal hypercapnia [209] and human breath-holding [157, 203, 210, 211] studies indicate that hypercapnic conditions are associated with global increases in most cortical and subcortical grey matter blood flow. Thus, we expect region-independent, nonspecific activation in all areas during IBH. In contrast, we expect region-dependent, specific activation or deactivation of BOLD signal intensity during SBQ.
- We expect main effects for the repeated measures, indicating significant differences in signal intensity across time.
- We expect no significant interactions.

D.6.5. State-related fMRI analysis (Hypotheses 4-5).

Sr-fMRI methodologies will be used to probe brain mechanisms during SBQ, IBH, and control periods. In the previous three analyses, we identified brain areas that displayed significant time-locked relation to the onset of both IBH and SBQ. A complementary approach to identification of brainstate changes is the use of state-related methodology. This method divides the time-series into condition-specific bins for comparison. Scans collected in Expt. 2 will be categorized into six bins: before and during either IBH, SBQ or equal-length periods during eyes-close (EC) control. Scans assigned to each bin will be compared by multiple linear regression, correcting for differences in blood gas levels across the three conditions.

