D.6.5.1. Sequence of Analysis. First, we will create a dummy time-series of 1, or 2's that correspond to the scans before and during three conditions: IBH, SBQ or EC. The dummy time-series then will be convolved with the hemodynamic response model using the Cohen Model. This will yield the dummy independent variable that will be entered into the multiple linear regression analysis along with O₂ and CO₂ data. The scans for each of the periods will be dependent variables in the analysis. We will examine the resulting statistical parameter maps for clusters of pixels displaying significant fluctuations in signal intensity. The Z-statistic of the activated clusters that meet our criteria (D.2.3.) will be entered as variates in a repeated-measures ANOVA, with brain area as the factor and the period as the repeated measures.

D.6.5.2. Comparison between conditions: SBQ, IBH and EC. Condition differences will be assessed with two-way repeated measures ANOVA with brain areas and condition as factors, and the two periods (before and during the conditions) as the repeated measures. Individual comparison will be conducted if there are significant main effects.

- We expect no main effects for brain areas, indicating highly variable activation across brain areas yielding no consistent relations.
- We expect main effects for condition (SBQ, IBH, EC), indicating different brain mechanisms are active during each condition. For example, during IBH we expect higher levels of task effort and motor system activation, and possibly higher CO₂ levels to yield the predicted main effect.
- We expect main effects for the repeated measure (before and during). The 'before' periods may be somewhat similar, while the 'during' periods may be significantly different.
- We expect significant interactions, indicating differential involvement of some brain areas during the three conditions. For instance, the cerebral cortex may exhibit lower BOLD signal in both 'before' periods. However, the cortex is expected to be activated during IBH, while remaining low or reduced during SBQ.

D.6.6. Outcome. This experiment will help identify:

- (1) Neural mechanisms specific to the generation and maintenance of IBH, and the effects of hypercapnia and loss of mechanical respiratory activity on BOLD signal intensity.
- (2) Neural mechanisms specific to SBQ periods, as compared to a variety of brainstates, including, other meditation periods, IBH, and EC.

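### Section D.6.4.3 predicts no interaction although Hypothesis 5 is one, and Hypothesis 7 has only the pre-SBQ scans as a proxy for non-SBQ meditation and no named contrast

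*Protocol*

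**What the plan says.** Hypothesis numbers follow Protocol Section A. Hypothesis 5 is D.6.1.3 and Hypothesis 7 is D.6.1.5; Section D.6 renumbers them locally as 3 and 5.

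- **Hypothesis 5 (Section A).** The SBQ pattern will "differ from IBH control periods in terms of reduced BOLD signal of the anterior cingulate cortex and brainstem during SBQ".
- **Its analysis (D.6.4.3).** "Er-fMRI will be compared between IBH and SBQ periods, using a repeated measures MANOVA". IBH is expected to activate all areas without regional specificity. "In contrast, we expect region-dependent, specific activation or deactivation of BOLD signal intensity during SBQ". The list of expected results contains a main effect of brain area, a main effect over time, and then "We expect no significant interactions". No condition effect is listed.
- **State-related comparison (D.6.5.2).** For SBQ, IBH and the eyes-closed control (EC), the plan expects no area main effect, but does expect main effects of condition and of before/during, and significant interactions. The follow-up rule is: "Individual comparison will be conducted if there are significant main effects".
- **Hypothesis 7 (D.6.1.5).** "BOLD signal intensity patterns during SBQ periods will differ from the scans during non-SBQ periods during meditation".
- **Its analysis (D.6.5, headed as covering it).** "Scans collected in Expt. 2 will be categorized into six bins: before and during either IBH, SBQ or equal-length periods during eyes-close (EC) control". D.6.5.1 begins: "First, we will create a dummy time-series of 1, or 2's that correspond to the scans before and during three conditions". The resulting clusters go into an ANOVA with brain area as factor and period as repeated measure. D.1 had described this method with three periods (before, during and after), and D.6.6 promises a comparison of SBQ with other meditation periods.

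**The concern.** D.6.4.3 describes an interaction and then predicts that none will be found. If the hypothesised reduction in anterior cingulate and brainstem appears in SBQ but not in IBH, the result supports Hypothesis 5 and at the same time fails the written expectation. A reader of the results could score it either way. In D.6.5.2 the predicted regional differences are expected to show as interactions, but an interaction alone does not trigger the comparisons that would locate them.

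Hypothesis 7 concerns meditation outside SBQ in general. The bins represent that state only by the scans leading into an SBQ. Section B.2.4.2 describes that stretch as the de-excitation process that ends in SBQ, so it is a selected substate. Following the plan would answer a narrower question than the hypothesis asks.

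**Working it through.** **1. Hypothesis 5: what the expected profiles imply.** Take k areas, IBH mean a in every area (flat) and SBQ mean b_j in area j, with average b̄.

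- Area main effect in area j: (a + b_j)/2 − (a + b̄)/2 = (b_j − b̄)/2. Its sum of squares over two conditions is Σ(b_j − b̄)²/2.
- Interaction in area j: +(b_j − b̄)/2 for SBQ and −(b_j − b̄)/2 for IBH. Its sum of squares is also Σ(b_j − b̄)²/2.

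So with a flat IBH profile the two are equal. Illustration with assumed values: six areas, IBH = 1 throughout, SBQ = −0.5, −0.5, 0, 0, 0.5, 0.5. Then b̄ = 0, Σ(b_j − b̄)² = 4 × 0.25 = 1, and area and interaction sums of squares are 0.5 each. If the interaction is set to zero with IBH flat, the area effect is zero too, against the first expectation in D.6.4.3. Flat IBH, region-dependent SBQ and no interaction cannot all hold. If time is kept as a factor and activation means change after onset, the same argument applies to condition x area x time.

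**2. The plan's own counts.** Bins: 3 conditions x 2 periods = 6, as stated. SBQ periods: 4 runs x 3 to 5 = 12 to 20, as stated in D.6.4.

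**3. Hypothesis 7: how much meditation enters a bin.** Inputs: four 5-minute meditation periods (D.6.3) = 1,200 s; 12 to 20 SBQs; duration 10 to 40 s (D.6.2). The length of the 'before' bin in D.6.5 is not stated. Two assumptions are shown: equal to the SBQ, or 12 s as in the event-related window of D.6.4. Unbinned time = 1,200 − SBQ time − 'before' time, not below zero.

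| SBQs x length | SBQ time | Unbinned, before = SBQ length | Unbinned, before = 12 s |
|---|---|---|---|
| 12 x 10 s | 120 s | 960 s (80%) | 936 s (78%) |
| 20 x 20 s | 400 s | 400 s (33%) | 560 s (47%) |
| 12 x 40 s | 480 s | 240 s (20%) | 576 s (48%) |
| 20 x 40 s | 800 s | 0 s (0%) | 160 s (13%) |

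Non-SBQ time is 400 to 1,080 s. With a 12 s bin, the 'before' scans hold 144/1,080 = 13% to 240/400 = 60% of it.

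**4. The regressor in D.6.5.1.** A series coded 1 for before and 2 for during, convolved and entered as one variable, yields at most one coefficient per condition. If only binned scans enter, with an intercept, that coefficient reflects during minus before. If unbinned scans enter as 0, it scales both periods together. In neither case are there two separately estimated values, one per period, for an ANOVA with period as repeated measure.

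**The case against.** The strongest reply is that an expectation is not an analysis rule. The sentence removes no term from any model, D.6.4.3 does compare SBQ with IBH, and D.6.4 adds a MANOVA on onset, latency and peak intensity by region for the two conditions. A reader might infer that Hypothesis 5 goes untested. That is not supported: both MANOVAs can show the regional difference. What stands is the wrong prediction and the absence of a named condition contrast. Limiting the sentence to area x time is possible, though the text does not say so, and it does not rescue it: a uniform post-onset response in IBH averaged with a region-varying one in SBQ still varies by area.

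A reader might also infer that the follow-up rule would block the anterior cingulate and brainstem finding. The rule belongs to D.6.5.2, not to D.6.4.3, and D.6.5.2 expects condition and before/during main effects, either of which would open the comparisons. Nor need opposing regional SBQ effects cancel the condition effect, because IBH is expected to be raised everywhere. The remaining defect is that the predicted interaction is not itself a trigger.

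Hypothesis 7 is not without any bin or contrast: scans before SBQ are non-SBQ meditation, and D.6.5.1 compares before with during. That is a partial proxy. The claim that the coding forces the before effect to half the during effect holds only if unbinned scans are coded 0, which the protocol does not say.

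Finally, C.2.6.3 warns of mixing substates, so a broad non-SBQ bin has its own drawback.

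**Conclusion.** The point holds as a set of inconsistencies to correct, not as a failure to analyse Aim 2.

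- **Hypothesis 5:** the contradiction in D.6.4.3 follows by algebra from its own expected profiles and needs no assumed effect size.
- **D.6.5.2:** interactions are predicted, but only main effects trigger follow-up.
- **Hypothesis 7:** it has a pre-SBQ proxy, no 'after' period, no bin for other non-SBQ meditation and no named contrast. The share of meditation time left out runs from none to about 80% if 'before' equals the SBQ length, or 13% to 78% with a 12 s window. The 80% is the sparse extreme (12 SBQs of 10 s) and should not be read as typical.
- **Coding:** one 1/2 regressor cannot feed a two-level period factor, whichever way unbinned scans are handled.

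Two of the seven stated hypotheses are affected. The study is exploratory and the scans would exist anyway, so this should be corrected before analysis but does not call the data collection into question. A statistical analysis plan, if one exists, may settle the coding; the contradictory expectation and the fixed six bins are in the protocol itself.

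**What to change.** 1. In D.6.4.3, delete the expectation of no interactions. Name the condition x area interaction in the post-onset response as the test of Hypothesis 5, with direct SBQ minus IBH contrasts in anterior cingulate and brainstem.
2. In D.6.5.2, let significant interactions as well as main effects open the individual comparisons.
3. In D.6.5, state the length of the 'before' bin and add separate bins for 'after SBQ' and 'other non-SBQ meditation'. Reconcile D.6.5 with the three periods described in D.1.
4. In D.6.5.1, give each bin its own 0/1 regressor convolved with the response model, so that before and during are estimated separately.
5. Name SBQ versus non-SBQ meditation as the Hypothesis 7 contrast, and report it alongside before versus during SBQ, because the 'other' bin may mix substates.

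Cost: changes of wording and a few more regressors. No extra scanning is needed, since the whole 5-minute meditation period of each run is recorded under D.6.3.

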We determined sample size of 10 subjects based on published neuroimaging studies [111, 186]. The fMRI meditation study of Lazar et.al. [143] reported significant results with five subjects. Two PET studies of meditation [142, 144] reported significant signal changes with nine and four subjects, respectively. Litscher's recent study of Qigong [187] examined cerebral blood flow using two subjects, but reported no estimates of significance. Newberg et.al. [73] neural SPECT study of Tibetan meditation reported significant blood flow changes with eight subjects. An examination of 50 reports on PET or fMRI imaging of hypnosis, acupuncture, complex cognitive tasks, or simple sensory and motor stimulation showed that statistical significance was found with 10 or less subjects [see for example, 108, 111, 162, 188, 189-199].

D.5. Examine the Patterns of Neural Activity during the De-Excitation Substate (Aim 1).

Experiment 1: Selection of epoch length and control condition to image the de-excitation process.

D.5.1. Hypotheses. We will be testing two hypotheses in this experiment.**D.5.1.1 Epoch length.** We hypothesize that the shorter epoch length in a ABC-cycling protocol (randomly-ordered meditation and controls) will best 'frame' the initial de-excitation process due to significantly higher signal-to-noise ratio, higher signal intensity and less variance in the statistical test;

D.5.1.2. Control conditions. We hypothesize significant differences in signal intensity across the three different epoch conditions—TM, passive-attending and mental-counting, including in rank order: de-excitation will be maximum for TM, then passive-attending, and lastly, mental-counting.

D.5.2. Issues.

D.5.2.1. Epoch length. Epoch length will be pre-framed during our subject selection protocol. We will examine two epoch lengths centered on this preliminary value. The best frame will include maximum duration of the de-excitation process without the actual onset of a SBQ for most of the meditation epochs.

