We will record fMRI (in first 10 subjects meeting inclusion criteria) during randomly ordered epochs of controls and TM practice. We will use two cycling ABC-run with eyes-closed. Each ABC-run comprises TM and two control conditions: (1) listening passively to nature (ie, ocean) sounds or (2) mental-counting by '2s'. An ABC-run (for example, using 30 sec epochs) will last about 22min, including 45 total epochs, 15 epochs each condition. This will result in 22 min/run x two epoch lengths = 45 min of testing, plus 40 min of preliminary anatomic scans, for a total time of less than 2 hr per MRI session. Whole-brain scans will be recorded from 19 slices per scan. At the end of each 22-min run, subjects will be asked to report their experiences. Carryover effects will be minimized by: (1) inserting one minutes breaks between runs. During these breaks we will be speaking and de-briefing the subjects; and (2) randomly presented control conditions in the same run. With this design, *within*-sets comparison will provide an estimate of the *minimal* carryover effects and *across*-sets will provide an estimate of *maximal* carryover effects.

D.5.4. Analysis for Hypotheses 1 & 2.

The data will be processed, and clusters of significant fluctuations in signal intensity will be noted (see Sect. D.2.2-D.2.3.). We expect clusters of fluctuations in signal intensity in 4-8 brain areas (see Sect. B.). The Z-statistics for areas of significant fluctuations in signal intensity will be noted from all runs and used as the variate in a repeated measures MANOVA. In this MANOVA, brain areas (4-8 estimate), and epoch condition (3) will be the factors, and the epoch-lengths (2) will be the repeated measure. For all main effects, individual comparisons will be conducted.

1. We expect **main effects for brain areas**, indicating significant differences in signal intensity between one or more brain areas. These changes may include in rank order: basal forebrain increases, slight cerebral and cerebellar cortex and mesencephalic reticular formation decreases, and no decreases in medial thalamus.
2. We expect **main effects for epoch condition**, indicating significant differences in signal intensity across the three different conditions—TM, passive-attending and mental-counting. These changes may include in rank order: de-excitation will be maximum for TM, then passive-attending, and lastly, mental-counting.

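### Protocol D.6.5.2 reads a predicted null brain-area main effect as showing variable, inconsistent activation, which that test cannot show, and ties follow-up comparisons to main effects only

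*Protocol*

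**What the plan says.** Protocol D.6.5.2 compares SBQ, IBH and EC by a "two-way repeated measures ANOVA with brain areas and condition as factors, and the two periods (before and during the conditions) as the repeated measures". The values analysed are described in D.6.5.1: "The Z-statistic of the activated clusters that meet our criteria (D.2.3.) will be entered as variates in a repeated-measures ANOVA".

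D.6.5.2 then lists four expectations. The first is "We expect no main effects for brain areas, indicating highly variable activation across brain areas yielding no consistent relations". The second and third predict main effects of condition and of period. The fourth is "We expect significant interactions, indicating differential involvement of some brain areas during the three conditions", and its example has cortex behaving differently by condition: "However, the cortex is expected to be activated during IBH, while remaining low or reduced during SBQ".

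Just before that list, the section says that individual comparisons will be made if main effects are significant. It names no follow-up for a significant interaction.

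On size, D.4.3 says "We determined sample size of 10 subjects based on published neuroimaging studies". No effect size, standard deviation or power is given for this ANOVA. The number of areas is not stated for Experiment 2; for Experiment 1, D.5.4 says "We expect clusters of fluctuations in signal intensity in 4-8 brain areas".

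**The concern.** The first expectation gives a non-significant F test a positive scientific meaning. The test asks only whether area means, averaged over conditions and periods, differ by more than chance. D.6.5.2 sets no margin, interval, variance component or between-subject measure that would turn a failure to reject into evidence of variability.

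Two things are at stake. First, a report could state that areas bear no consistent relation to state when the data are equally compatible with a uniform response, with a reproducible pattern that changes sign between conditions, or with too few subjects. Second, D.6.6 names mechanisms specific to SBQ as an outcome. The predicted result is a null area effect with significant interactions. Under the rule for individual comparisons, that result would open comparisons among conditions and between periods, but none by area. Area-level comparison is the step that would show where SBQ differs.

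**Working it through.** There is no protocol figure to reproduce, because none is stated for this ANOVA. The check asks how often the area test is non-significant under different true states.

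**Inputs from the protocol**
- n = 10 subjects (D.4.3).
- Three conditions and two periods (D.6.5.2).
- k = 4 to 8 areas, carried over from Experiment 1 (D.5.4) as an assumption.

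**Assumptions not in the protocol**
- Two-sided alpha of 0.05 and sphericity.
- Normal errors.
- Effect size f = SD of the true area means ÷ SD of the subject-by-area error.

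**1. Why the average hides the pattern.** Let area j respond by v_j in SBQ, −v_j in IBH and 0 in EC. Its mean over conditions is (v_j − v_j + 0)/3 = 0 for every j, however large v_j is and however many subjects share it. If instead every area responds by the same amount m, every area mean is m and the differences between areas are again 0. In both cases the area null hypothesis is true, so the test is non-significant with probability 1 − 0.05 = 95%.

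**2. Simulation of that point.** Subject × area × condition layout, n = 10, 4,000 runs per scenario, period omitted:

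| True state | Area test non-significant, k = 4 / 6 / 8 | Area × condition significant, k = 4 / 6 / 8 |
|---|---|---|
| Activation inconsistent across subjects | 95.2 / 94.6 / 95.3% | 5.5 / 5.2 / 5.0% |
| Uniform activation in all areas | 95.2 / 95.4 / 94.9% | 4.8 / 4.8 / 5.3% |
| Mirror patterns in SBQ and IBH (large assumed crossover) | 95.0 / 95.4 / 95.4% | 99.9 / 100 / 100% |

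The area test cannot separate the three rows. The interaction test picks out the third but does not separate the first two.

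**3. Real, consistent area differences with 10 subjects.** Non-central F with d1 = k − 1, d2 = 9(k − 1) and λ = 10·k·f². For k = 6 and f = 0.3: d1 = 5, d2 = 45, λ = 10 × 6 × 0.09 = 5.4, and the test is non-significant in 65% of trials. The full set:

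| f | λ, k = 4 / 6 / 8 | Non-significant, k = 4 / 6 / 8 |
|---|---|---|
| 0.25 | 2.5 / 3.75 / 5.0 | 79 / 76 / 72% |
| 0.30 | 3.6 / 5.4 / 7.2 | 72 / 65 / 59% |
| 0.40 | 6.4 / 9.6 / 12.8 | 52 / 41 / 31% |
| 0.50 | 10 / 15 / 20 | 31 / 18 / 11% |

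**4. The follow-up rule applied to the predicted result.** Area main effect: predicted null, so no comparisons between areas. Condition and period main effects: predicted significant, so comparisons of conditions and of periods. Interactions: predicted significant, but no follow-up is named. The predicted outcome therefore ends without a specified comparison of conditions within an area.

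**The case against.** The strongest reply is that the sentence is one of four parallel expectations, not a decision rule. No passage says that a null area effect will be reported as a finding. The hypotheses tested here concern SBQ against IBH, control or non-SBQ periods, not areas averaged over conditions. The study is exploratory, and a test of interactions is already planned. All of that stands, and it limits the weight of the point.

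The figures also deserve caution. The 95% values are simply 1 − alpha. The others rest on assumed effect sizes. The model ignores the period factor, and also ignores that the Z-statistics entered have already passed the selection threshold in D.2.3.

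Two stronger readings are tempting, and the documents support neither:

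- A reader might infer that the interpretation runs in the wrong direction, since activation that differs between areas should produce an area effect. That holds only if variable means fixed differences between areas. If it means inconsistent across subjects or conditions, which the rest of the sentence suggests, a null is what one would expect. The fault is that the null does not identify that explanation.
- A reader might infer a contradiction with D.6.4.3, which expects area main effects, no interactions, and "In contrast, we expect region-dependent, specific activation or deactivation of BOLD signal intensity during SBQ". That section is an onset-locked comparison of SBQ and IBH. D.6.5.2 adds EC, uses before/during bins and adjusts for blood gases. Different averages can have different expectations.

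It can also be said that the statistical parameter maps would still display SBQ clusters. They would, but a map inspected by condition is not a comparison of conditions within an area.

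**Conclusion.** The point holds as a minor-to-moderate correction of interpretation. A non-significant area main effect in D.6.5.2 supports no conclusion about variability or consistency, because uniform responses and condition-reversed patterns give the same null about 95% of the time. The planned interaction test helps with a sizeable reversal, but it cannot separate uniform from inconsistent activation or rule out limited power. How much limited power contributes is unknown: the range of 11% to 79% depends on the assumed f of 0.25 to 0.50, on 4 to 8 areas, and on an unselected normal-error model.

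The practical consequence lies in the follow-up rule. As written, it specifies no area-level comparison for the very result that the section predicts. This rests on reading the rule as tying each set of comparisons to its own main effect. If a significant condition effect were meant to open comparisons within areas, the text should say so. No hypothesis, test or data collection is invalidated.

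**What to change.** In D.6.5.2:

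1. Delete the clause that interprets the null, and state that a non-significant area main effect supports no conclusion about variability across areas.
2. Let a significant interaction involving area (area × condition, or area × condition × period) trigger individual comparisons as well as significant main effects.
3. Report, for each area and condition, the during-minus-before change with its 95% confidence interval.
4. If consistency is to be claimed, estimate it directly: the between-subject SD of the change in each area, or the number of the 10 subjects who share its sign.

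The cost is a few lines of text and one summary table from data already in the analysis, with no new scans or subjects. The downside is a larger number of area-level comparisons, which should be labelled exploratory.
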